Study title: Could Apnea Induce Hypoalgesia? An Explorative Randomized Controlled Trial.

Date uploaded: 27/02/2023.

Statistical analysis.

Shapiro-Wilks test was employed to examine normal data distribution between groups for all variables. According to its results, T-test for independent samples or Mann-Whitney U tests were employed to examine differences between groups in baseline data.

Repeated measures ANOVA was employed to test time, group and time x group interaction effects on pressure pain threshold (PPT) for the dorsal distal-phalange base of the thumb dominant arm and tibialis anterior muscle belly of the dominant leg, respectively.

Repeated measures ANOVA was also employed for evaluating conditioned pain modulation (CPM) responses for upper limbs, analysing basal and conditioned PPT before and after interventions. Time, group, and time x group interaction effects were explored.

Arterial oxygen saturation, and heart rate (HR) response were explored with a repeated measures ANOVA, with the basal and during-training values between groups, for mean partial oxygen saturation (SpO_2), minimum SpO_2 , mean $\%HR_{max}$, and peak $\%HR_{max}$ were explored. Times through the 4 hypoxemia zones and 5 $\%HR_{max}$ zones were explored for pairwise differences between groups with T-Student test for independent samples or Mann-Whitney U test.

According to normal distribution analysis, Spearman rank or Pearson tests were used to evaluate linear correlations between PPT post-preintervention changes and the following variables: (1) basal CPM response (difference between conditioned and unconditioned pre-intervention PPT); (2) rated perceived exertion (RPE); (3) mean SpO_2 , minimum SpO_2 value, and time in the 4 hypoxemia zones; (4) mean $\%HR_{max}$, peak $\%HR_{max}$, and time in the 5 zones of $\%HR_{max}$. All these correlation analyses were explored only in the apnoea group. As a secondary objective we aimed to establish associations between RPE and HR and SpO_2 in the apnoea group.

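### Basal CPM is correlated with PPT change in the apnoea group only, so the coefficient cannot separate prediction of response to apnoea from a possible shared-baseline artefact or from change that also occurs in controls

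*SAP*

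**What the plan says.** The SAP is one section, Statistical analysis. Its last paragraph plans "linear correlations between PPT post-preintervention changes and the following variables", and the first variable listed is "basal CPM response (difference between conditioned and unconditioned pre-intervention PPT". RPE, the SpO2 measures and the %HRmax measures follow. It then states: "All these correlation analyses were explored only in the apnoea group".

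Earlier paragraphs use both groups. The second reads "Repeated measures ANOVA was employed to test time, group and time x group interaction effects on pressure pain threshold (PPT", for the thumb and for tibialis anterior. The third describes "evaluating conditioned pain modulation (CPM) responses for upper limbs, analysing basal and conditioned PPT before and after interventions", again with group and time x group effects. The fourth covers SpO2 and %HRmax "with the basal and during-training values between groups".

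Control data for PPT change and basal CPM are therefore already in the planned analysis. The SAP gives no reason for leaving them out of the correlations. It also does not say whether the unconditioned pre-intervention PPT in the CPM term is the same reading as the pre value in the change score.

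**The concern.** There are two separate difficulties, and both are clearest for basal CPM.

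The first is possible mathematical coupling. Basal CPM subtracts an unconditioned pre-intervention PPT, and the outcome subtracts a pre-intervention PPT. If these are one reading, its error enters both differences with the same sign. A reading that happens to be low then raises both basal CPM and the apparent change, which produces a positive correlation whether or not CPM has anything to do with apnoea. CPM is assessed on the upper limbs, so sharing is plausible for the thumb. Tibialis anterior has its own baseline and is not directly coupled.

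The second does not depend on sharing. Within one arm, people with higher basal CPM may show larger PPT change for reasons that also operate in controls. An apnoea-only coefficient cannot tell that from prediction of the response to apnoea.

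At stake is how one exploratory association is read. The randomised comparison of PPT is unaffected.

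**Working it through.** **No figure to reproduce.** The SAP states no sample size, SD, correlation or significance level for this analysis. All numerical inputs below are assumptions: 15, 20 or 25 per arm, a two-sided 5% level, normal data and independent reading errors of equal variance, set to 1. The two difference scores are taken from the SAP.

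**Model with a shared reading and no true link.** Let T be a person's true PPT, D true CPM with variance k, d true individual variation in change with variance v and independent of D, and e1, e2, e3 the reading errors.

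- Unconditioned pre = T + e1; conditioned pre = T + D + e3; post = T + group shift + d + e2.
- Basal CPM = D + e3 − e1, with variance k + 2.
- PPT change = shift + d + e2 − e1, with variance v + 2.
- Covariance = var(e1) = 1, although D and d are unrelated.
- Correlation r = 1/√((2 + k)(2 + v)); slope of change on basal CPM = 1/(k + 2).

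**Expected r and simulated rejection by the apnoea-only Pearson test:**

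| k | v | Expected r | n = 15 / 20 / 25 |
|---|---|---|---|
| 0 | 0 | 1/√4 = 0.50 | 50 / 64 / 75% |
| 0 | 2 | 1/√8 = 0.35 | 26 / 35 / 43% |
| 2 | 0 | 1/√8 = 0.35 | 26 / 34 / 42% |
| 2 | 2 | 1/√16 = 0.25 | 15 / 19 / 23% |
| 8 | 0 | 1/√20 = 0.22 | 12 / 16 / 19% |
| 8 | 2 | 1/√40 = 0.16 | 9 / 10 / 12% |

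Repeat simulations differ by up to about one percentage point, so the ranges are approximate: 14 to 42% at k = 2 and 9 to 19% at k = 8. The first row is the upper end, because it allows no true variation in CPM or in change.

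**Sensitivity.**
- Spearman, which the SAP allows, rejects slightly less often. With v = 0 it gives 42/58/69% (k = 0), 23/29/38% (k = 2) and 10/15/18% (k = 8).
- An error common to all readings on one occasion cancels in basal CPM but not in change. With variance equal to reading error and v = 0, r = 1/√(4(2 + k)) = 0.35, 0.25 and 0.16 for k = 0, 2 and 8.
- With separate pre-intervention readings the rejection rate is about 5%.

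**What the control arm adds.** The built-in slope 1/(k + 2) is 0.50, 0.25 and 0.10 for k = 0, 2 and 8. It involves baseline quantities only, so randomisation makes it equal in expectation in the two arms, and the slope difference removes it. The simulated slope contrast (pooled residual variance, 2n − 4 df) rejects about 5% throughout. The correlation also contains v, which apnoea may change, so the arms should be compared on slopes rather than on r.

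**Precision of that contrast.** With a true extra slope of 0.5 on true CPM in the apnoea arm and v = 0, power is 16/21/26% at k = 2 and 34/46/55% at k = 4.

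**The case against.** The strongest objection is that the SAP does what it says. The trial is labelled explorative, the restriction is stated openly, and the coefficients are valid descriptions of what PPT change tracks among people doing apnoea. This stands. A reader might infer that the SAP claims apnoea specificity, or that the restriction undermines the trial's main comparison. The text supports neither: it makes no specificity claim, and the correlations do not feed the group analyses.

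Next, coupling depends on a fact that the SAP does not give, and baseline reading procedure is commonly left to a protocol. This also stands. It would be wrong to call the thumb correlation spurious; it may be inflated if the reading is shared. Coupling is in any case a fault of the shared reading rather than of leaving out controls, and using separate readings removes it at source.

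Third, a control coefficient read on its own would mislead. At k = 2 with v = 0, among runs where the apnoea coefficient is falsely significant, the control coefficient is non-significant in about 75/65/58% at 15/20/25 per arm. That could pass for specificity. The remedy must therefore rest on the slope difference and its interval, not on significance arm by arm.

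Finally, limiting the HR and SpO2 correlations to the exposed arm is defensible. Both arise after randomisation, so a between-arm slope contrast is not protected by it, and controls may vary too little in SpO2 to estimate a slope. The point should not be widened to every correlation on the list.

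**Conclusion.** The point holds for basal CPM as a minor, inexpensive improvement. In the apnoea arm alone, the coefficient cannot show that CPM predicts response to apnoea rather than PPT change in general. For the thumb it may also carry a positive artefact.

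The size of that artefact rests wholly on assumptions: a shared reading, independent normal errors of equal variance and 15 to 25 per arm. Within them, false rejection runs from about 9% to a ceiling of 75%, and the upper figures need little true variation in CPM and in change. With separate readings the artefact disappears and only the question of interpretation remains. Confidence is moderate, because the SAP leaves the deciding fact open.

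**What to change.** - **Basal CPM.** Fit the same association in the control group, and report the group x basal CPM slope difference with its 95% CI as the exploratory estimate. State that apnoea specificity will not be inferred from significance in one arm only.
- **Baseline reading.** State whether the thumb pre-intervention PPT is the same reading in the CPM term and the change score. Where separate baseline readings already exist, use different ones for the two. Otherwise interpret the thumb coefficient only beside the control one.
- **Other correlations.** Keep them in the apnoea group and label them descriptive. A control counterpart is optional for %HRmax, and for SpO2 only if controls vary enough, with a note that both arise after randomisation.

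The cost is a few sentences in the SAP and one or two regressions on data already being analysed. The drawback is the imprecision of the slope contrast shown above, which is why it belongs in the report as an estimate with an interval.
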